4.4 IL-12 pDNA adjuvant

The GENEVAX® IL-12 DNA plasmid is a dual promoter expression plasmid which expresses the genes encoding human IL-12 subunits p35 and p40 under separate regulatory control. The p35 subunit is under the control of the hCMV promoter/enhancer and the SV40 polyadenylation signal. The p40 subunit is under the control of the sCMV promoter and the BGH polyadenylation signal. The plasmid contains a chimeric kanamycin resistance gene and a pUC bacterial origin of replication. The *IL-12* pDNA adjuvant is be produced at a concentration of 2 mg/mL and is formulated in 30 mM citrate buffer pH 6.5 containing 150 mM NaCl, 0.01% EDTA, and 0.25% bupivacaine-HCl. The plasmid is formulated in bupivacaine to enhance stability and facilitate entry into cells [72]. It was manufactured by Ajinomoto Althea, San Diego, CA.

The *IL-12* pDNA adjuvant will be given together with the p24CE1/2 pDNA, the p55^{gag} pDNA and the p24CE1/2 and p55^{gag} pDNA combination, respectively and will be delivered with electroporation (EP). HVTN 080, a phase 1 clinical trial, has demonstrated

the safety and immunogenicity of 3 mg PENNVAXTM-B (*gag, pol, env*) vaccine (Inovio Pharmaceuticals, Inc.) with 1 mg *IL-12* pDNA (Profectus BioSciences, Inc.) given by IM/EP [75]. In addition, recent work by [name], [name] and colleagues has shown induction of immunity with the proposed vector given with *IL-12* pDNA EP in rhesus macaques, with superior CD4⁺ and CD8⁺ T-cell as well as Ab responses [76-78]. Other clinical trials (HVTN 087, IAVI B004) have shown reduced CD4⁺ T-cell response rates in groups given *IL-12* pDNA, while CD8⁺ T-cell responses were equivalent or improved, compared to study arms without *IL-12* pDNA [79,80]. The *IL-12* pDNA adjuvant, GENEVAX® IL-12 DNA Plasmid, has been tested by the HVTN in 5 previous trials: HVTN 060 (DAIDS-ES ID 10057, BB IND#12367), HVTN 063 (DAIDS-ES ID 10058, BB IND#12439), HVTN 070 (DAIDS-ES ID 10490, BB IND#13449), HVTN 080 (DAIDS-ES ID 10741, BB IND#14116), and HVTN 087 (DAIDS-ES ID 11673, BB IND#14976). Please refer to the Investigator's Brochure (IB) for additional information.

4.5 Electroporation (EP)

EP has been shown to be an efficient means to introduce DNA into cells [81]. EP is a technology in which a transient electric field is applied to the target tissue in order to enhance the cellular uptake of large molecules such as DNA. EP works by temporarily increasing the permeability of cell membranes. Although EP has been used experimentally in humans [82,83]. EP remains investigational. Preclinical and phase 1 studies have suggested that EP enhances the potency of pDNA vaccines [80,84-87]. Ichor Medical Systems has focused on the development of EP technology where the means for agent administration and electric field application are integrated into a fully automated administration device. The overarching goal of this approach, embodied in the Ichor TDS-IM, is to enable agent administration, placement of electrodes, and timing of EP delivery to be completed in a simple, user independent fashion. Each TDS-IM device consists of three components, a single use Application Cartridge housing the EP electrodes and the agent of interest, a handheld, multi-use Integrated Applicator, and a Pulse Stimulator. The TriGrid[™] electrode array for intramuscular delivery consist of four electrodes arranged in two triangles to form a diamond shape around an integrated central injection needle. Correlation of the electrode configuration with the agent distribution pattern intrinsic to the target tissue ensures that the EP effect is induced only in tissues where the agent of interest has been distributed, improving tolerability and minimizing tissue disruption. To date, the TDS-IM has been used for IM delivery of DNA vaccines or placebo in over 20 human clinical studies totaling in more than 700 clinical trial participants. The device has been used for administration of pDNA doses of up to 4.0 mg per site and 8.0 mg overall. Use of the device has been associated with mild to moderate injection site reactions resolving within 24-72 hours. Other mild or moderate transient adverse events have included paresthesia or hypoesthesia in the injected limb, cutaneous bleeding, bruising, or hematoma, vasovagal reactions, flu-like symptoms, headache, fever, nausea, chills, dizziness, malaise, fatigue, arthralgia, myalgia, neuralgia, and CPK increase. One event of brief syncope has been reported in a person with pre-existing bradycardia. No serious pDNA or device related adverse events have been reported during these studies. Although the use of EP administration is associated with substantially more acute discomfort than a conventional injection, to date, study subjects have exhibited a high degree of compliance.

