The HVTN is also evaluating PENNVAX®-GP (Gag, Pol, Env) pDNA Vaccine and *IL-12* plasmid (INO-9012, Inovio Pharmaceuticals, Inc. Plymouth Meeting, Pennsylvania, USA), delivered via intradermal or IM/EP (CELLECTRA® EP system) in HVTN 098 (BB IND #16398, held by DAIDS). In that study, for IM delivery, the dose of PENNVAX®-GP is 8 mg and the dose of the Inovio *IL-12* plasmid is 1 mg, at a single injection site. The study is ongoing. No SAEs related to vaccination have been reported. Injection site pruritus has been reported by 19.1% of participants and presyncope following the vaccination procedure in 5.3%. Another *IL-12* pDNA (pUMVC3-hIL-12-NGVL3, City of Hope Center for Biomedicine and Genetics, Duarte, CA) has been given in doses up to 5.8 mg per administration delivered with EP directly into melanoma tumors, with no dose limiting systemic toxicities noted [91]. Hence, we do not anticipate any significant systemic or local adverse effects related to the use of *IL-12* pDNA IM with EP at the proposed dose.

Taken together, the studies suggest that *IL-12* pDNA delivered with plasmid DNA vaccines with EP may have a dose-dependent adjuvant effect on CD8+ responses. *IL-12* pDNA has been given at doses up to 1 mg at a single injection site with IM/EP and up to 1.5 mg total IM/EP at one visit (2 injection sites). Given the focus of this study on evaluating cellular immune responses, *IL-12* pDNA may provide an advantage to the evaluation of immunogenicity of the p24CE and p55^{gag} pDNA vaccines.

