4.11 Potential risks of study products and administration

Common	• Mild transient cutaneous bleeding, bruising/ecchymosis				
	• Mild to moderate injection site pain, tenderness, pruritus, erythema, or swelling/induration/edema				
	 Malaise/fatigue, myalgia, or headache in the first few days following injection 				
Less common	Severe injection site pain or tenderness				
	• Transient paresthesia or hypoesthesia in the injected limb				
	• Fever, chills, flu-like syndrome, arthralgia, rash, nausea, or dizziness in the first few days following injection				
	 Vasovagal reaction/lightheadedness/dizziness related to the injection procedure 				
	Transient changes in clinical laboratory values				
	• Injection site hematoma, laceration, bruising/ecchymosis, other transient lesions, itching, or bleeding related to the injection procedure				
	• A vaccine-induced positive HIV antibody test result				
Uncommon or rare	• Severe localized injection site reaction, such as sterile abscess or secondary bacterial infection				
	 Allergic reaction, including rash, urticaria, angioedema, bronchospasm, or anaphylaxis 				
	Muscle damage at the injection site				
	• Injection needle contact with the bone				
	Difficulty removing EP device				
	• Syncope				
Theoretical risks	Autoimmune disease or cancer				
	• Electrical injury with EP				
	• Disruption of function of implanted electronic medical devices with EP				
	• Exacerbation of cardiac arrhythmias with EP				
	• Effects on a participant's response to an approved HIV vaccine administered in the future				
	• Effects on susceptibility to HIV, if the participant is exposed to HIV				
	• Effects on the course of HIV infection/disease, if the participant is infected with HIV				
	• Effects on the fetus and on pregnancy				

Table 4-4 Summary of potential risks of study products and administration

5 Objectives and endpoints

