5.1 Primary objectives and endpoints

Primary objective 1:

To evaluate the safety and tolerability of the HIV-1 pDNA vaccines p24CE1/2 and $p55^{gag}$ administered with *IL-12* pDNA by intramuscular injection with electroporation

Primary endpoints 1:

- Frequency and severity of local injection/EP site and systemic reactogenicity signs and symptoms
- Frequency of AEs categorized by MedDRA body system, MedDRA preferred term, severity and assessed relationship to study products. Detailed description of all AEs meeting DAIDS criteria for expedited reporting
- The distribution of values of safety laboratory measures at baseline and at follow-up visits post vaccination
- Number of participants with early discontinuation of vaccinations and reason for discontinuation
- Magnitude of local injection/EP site pain as measured by a visual analog scale
- Distribution of responses to questions regarding acceptability of study injection procedures

Primary objective 2:

To compare the two pDNA prime/boost strategies with respect to breadth (defined as the number of targeted CEs) of $CD4^+$ and $CD8^+$ T-cell responses to conserved regions of the $p24^{Gag}$ protein

Primary endpoint 2:

The number of targeted CEs by CD4⁺ and CD8⁺ T-cell responses measured by ICS 2 weeks after the second and fourth vaccinations

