9.9.1 Assessment of systemic and local symptoms

Systemic symptoms include increased body temperature, malaise and/or fatigue, myalgia, headache, chills, arthralgia, nausea, and vomiting. Local symptoms include pain and/or tenderness proximal to the injection site. The daily maximum severity reached for each symptom during the assessment period is reported.

Body temperature is measured by oral or infrared thermometry and reported in degrees Celsius. If temperature is measured in Fahrenheit, the conversion to Celsius should be documented in the participant's chart note. A measurement is taken once daily during the assessment period and should be repeated if participant is feeling feverish.

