9.9.2 Assessment of injection site

Typical injection site reactions are erythema/redness and induration/swelling. The maximum horizontal and maximum vertical measurements for all injection site reactions are recorded.

All injection site reactions are monitored until resolution. Areas greater than 25 cm² are followed daily; otherwise, the frequency of follow-up is based on clinician judgment.

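### Reactions the protocol expects with electroporation are not named as solicited items, so the reactogenicity endpoint for the injection/EP site can under-ascertain them

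*Protocol*

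**What the plan says.** **What is expected.** Section 4.5 summarises experience with this device: "Other mild or moderate transient adverse events have included paresthesia or hypoesthesia in the injected limb, cutaneous bleeding, bruising, or hematoma, vasovagal reactions". The same sentence goes on to dizziness and neuralgia, among others. Table 4-4 (Section 4.11) carries these into the trial's own risk list. Under common risks it has "Mild transient cutaneous bleeding, bruising/ecchymosis" and also injection-site pruritus. Under less common risks it has "Transient paresthesia or hypoesthesia in the injected limb" and vasovagal reaction, lightheadedness or dizziness.

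**What is measured.** The first primary safety endpoint in Section 5.1 is "Frequency and severity of local injection/EP site and systemic reactogenicity signs and symptoms". Section 9.9.1 names eight systemic symptoms: raised temperature, malaise/fatigue, myalgia, headache, chills, arthralgia, nausea and vomiting. On the local side it says "Local symptoms include pain and/or tenderness proximal to the injection site". Section 9.9.2 says "Typical injection site reactions are erythema/redness and induration/swelling", and asks for dimensions of every injection-site reaction. Section 9.9 adds vaccine-related lesions, without defining them, and lymph nodes. It sends events not listed on a case report form (CRF) to the adverse experience log.

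**How it is analysed.** SAP 8.3.1 tabulates each reactogenicity sign or symptom by severity and arm. It forms maximum-severity composites for pain/tenderness, induration/erythema and systemic symptoms, and applies Kruskal-Wallis tests to severity. A separate primary endpoint is "Frequency of AEs categorized by MedDRA body system, MedDRA preferred term, severity and assessed relationship to study products".

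**The concern.** The endpoint is worded to cover the EP site as well as the injection, and EP is what separates this procedure from a plain injection. The protocol predicts certain EP reactions, some of them common, and then leaves them off the list that feeds that endpoint.

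Solicited and unsolicited collection are not equivalent. For a solicited item, a blank on a given day means the participant was asked and had nothing to report. For an unsolicited one, absence cannot be told from not having been asked, and the rate can depend on how closely each site probes. At stake is how well the trial can describe the frequency and severity of short-lived EP reactions.

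**Working it through.** No figure in the plan is in dispute, so the check is mainly a side-by-side reading.

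**1. Expected reactions against named items**

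| Reaction | Section 4.5 | Table 4-4 | Named in 9.9.1–9.9.2 | Where it goes as written |
|---|---|---|---|---|
| Limb paresthesia/hypoesthesia | yes | less common | no | AE log |
| Vasovagal reaction, dizziness | yes | less common | no | AE log |
| Bleeding, bruising, hematoma | yes | bleeding/bruising common; hematoma less common | no | unclear: lesion, site reaction or AE log |
| Injection-site pruritus | no | common | no | AE log |
| Headache, fever, nausea, chills, malaise/fatigue, arthralgia, myalgia | yes | common or less common | yes | reactogenicity CRF |

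The general symptoms from Section 4.5 are solicited. None of the four groups in the first four rows is. The last column assumes that the CRF, which is not among the documents, follows the protocol text.

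**2. Consequence for the analysis.** An event in the AE log is graded with the same DAIDS table (Section 11.2.2). It does not get the daily maximum grade required by Section 9.9.1, and it does not enter the reactogenicity tables or composites of SAP 8.3.1, 9.1 and 9.3.

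**3. Timing.** Section 4.5 says injection-site reactions with this device resolve within 24–72 hours and calls the other events transient. From the days in Appendix F, the gap from vaccination to the next clinic visit is:
- vaccination 1: 14 − 0 = 14 days
- vaccination 2: 35 − 28 = 7 days
- vaccination 3: 98 − 84 = 14 days
- vaccination 4: 175 − 168 = 7 days

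In between, Section 9.9 requires one staff contact on days 1–3, and the participant keeps a memory tool. A reaction that resolves within three days and is not on that tool depends on spontaneous mention or an open question.

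**4. Size.** The nearest stated figure is in Section 6.1.1: with 25 per vaccine arm, a 90% chance of at least one event at a true rate of 8.8%. It reproduces: 1 − (1 − 0.088)^25 = 0.900. That statement concerns serious or expedited events and assumes that every event occurring is observed. The documents give no rate at which unsolicited EP reactions are reported, so no corresponding figure can be derived for them.

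For scale only, Section 4.10.3 says of HVTN 098: "Injection site pruritus has been reported by 19.1% of participants and presyncope following the vaccination procedure in 5.3" (also a percentage). That trial used a different EP device and included intradermal delivery, and the text does not say whether those events were solicited. The rates cannot be carried over.

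**The case against.** The case against is substantial, and most of it stands.

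- **The events stay in the primary safety assessment.** AE frequency is itself a primary endpoint. SAP 9.1 and 9.3 give both the Safety Monitoring Board and the final report a table of EP-device-related AEs by preferred term and severity, plus a listing.
- **Staff are present or in contact.** Participants are observed after vaccination and assessed at 25–60 minutes (Section 9.3), contacted on days 1–3, and asked about AEs at every visit. An immediate vasovagal event would probably be seen. This does less for later paresthesia, pruritus or bruising.
- **EP-specific data are collected.** A pain scale is completed immediately after EP and twice more, and an EP acceptability questionnaire is given at four visits. A reader might infer that only ordinary-injection symptoms are solicited; these two primary endpoints show otherwise. The scale measures pain only, and the questionnaire's items are not shown.
- **Bruising may already be captured**, since erythema and induration are given as typical rather than exhaustive and all site reactions are measured.
- **All arms receive EP**, placebo included (Section 4.6.3), so the vaccine–placebo contrast is less exposed. It is not fully protected: active product contains bupivacaine and placebo is saline, so limb numbness could differ by arm, though the documents report no such difference.
- **Soliciting more items might blur the safety rules.** This does not hold up. The exemption in footnote b of Table 11-1 is a closed list that new items would not join, and the exception in Section 7.3.3 turns on symptoms being subjective, not solicited.

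A reader might also infer that the endpoint does under-count these reactions, by some calculable fraction. That goes beyond the text, which shows a less sensitive route of collection but no measured loss.

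**Conclusion.** The point holds as a gap in ascertainment. Reactions that the protocol expects with EP are not named as solicited items, so the reactogenicity endpoint can under-ascertain them when they are transient. Paresthesia/hypoesthesia, dizziness/presyncope and pruritus fall to unsolicited AE reporting; the route for bleeding and bruising is undefined. The size cannot be computed from the documents. The main effect is on the absolute description of EP tolerability, with less effect on comparisons between arms.

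The conclusion assumes that the CRF and memory tool mirror Sections 9.9.1–9.9.2. If they already list these items, what remains is to align the protocol and SAP text with them. This is an inexpensive improvement to a primary endpoint and does not mean that the safety assessment fails.

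**What to change.** **Protocol, memory tool and reactogenicity CRF.** Add four item groups to Sections 9.9.1/9.9.2 as solicited day 0–7 items graded by the DAIDS table:
1. paresthesia/hypoesthesia of the injected limb
2. injection-site pruritus
3. injection-site bleeding, bruising or hematoma
4. dizziness/presyncope, including vasovagal reaction

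State in Section 9.9 whether vaccine-related lesions include the third group.

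**SAP.** Tabulate the four groups by arm as separate rows under 8.3.1 and in the 9.1 and 9.3 reactogenicity tables. Leave the existing composites as they are, so that comparison with other trials is kept.

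**Safety rules.** State explicitly that adding the items does not alter the pause and AE-review rules in Table 11-1 or the discontinuation rules in Section 7.3.3. No change to either is proposed here.

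**Cost.** A few more lines on the memory tool and CRF and a few table rows, with no added visit or procedure. Reported rates will look higher than in trials that did not ask. Under Section 9.9, listed items with onset in the window go to the log only if they meet the serious or expedited-reporting criteria. The device-related AE tables would then hold fewer of these events, and the SAP should say that the two sets of tables are to be read together.

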4.6 Trial design rationale

One major goal of the proposed phase 1 trial is to demonstrate that a DNA plasmid expressing the CE regions of p24^{Gag}, given with *IL-12* pDNA adjuvant and IM/EP delivery, has an acceptable safety profile.

The proposed trial is also designed as a proof-of-concept demonstration that conserved elements of the viral $p24^{Gag}$ protein, normally subdominant in HIV infections, can be immunogenic, can induce levels of immune response comparable to full-length Gag, can potently shift the immunodominance of Gag epitopes from variable to conserved regions of the $p24^{Gag}$ protein when used in a CE/CE+*gag* prime/boost vaccination regimen, and can induce increased levels of polyfunctional and cytotoxic T cells directed to CE compared to the full-length Gag antigen administered as a pDNA vaccine. *IL-12* pDNA delivered with plasmid DNA vaccines with EP may have an adjuvant effect on CD8+ responses and provide an advantage to the evaluation of immunogenicity of the p24CE1/2 and p55^{gag} pDNA vaccines.

4.6.1 Dose (amount and number)

The DNA vaccines (p24CE1/2, p55^{gag}) will be given at 4 mg total dose per vaccination (2 mg per deltoid). Doses of DNA vaccines previously given in HVTN studies with IM/EP have ranged from 3 mg to 8 mg. Multiple priming vaccinations are proposed to increase the likelihood of robust immune responses.

GENEVAX[®] IL-12 DNA plasmid will be given at 2 mg total dose per vaccination (1 mg per deltoid). Doses of *IL-12* pDNA adjuvant previously given in HVTN studies with IM/EP have ranged from 0.25 mg to 1.5 mg, with up to 1 mg given at a single injection site.

In HVTN 080 (see Section 4.10.3), which showed an increase in ICS response rates (not statistically significant, possibly due to small sample sizes), 1 mg *IL-12* pDNA was given at a single site, and well-tolerated. In other studies, the local dose of *IL-12* pDNA was 0.25 to 0.75 mg. An adjuvant effect appears to be dose dependent on the local IM dose, and 1 mg per injection site has been chosen for this study, to try to replicate the adjuvant effect seen in HVTN 080. *IL-12* pDNA has not been associated with severe

reactogenicity or serious adverse events with up to 1.5 mg total dose per vaccination visit in these studies. We expect the minimal increase to 2 mg total dose (1 mg per injection site) to be safe and well tolerated both at the injection sites and systemically.

4.6.2 Prime-boost regimen

A prime-boost regimen of 4 vaccinations will be given, with injections at 0, 1 (priming immunogen) and 3, 6 months (booster immunogen(s)). This schedule allows for comparison with other HVTN studies of DNA vaccines given with IM/EP, which vaccinated participants on schedules of 0, 1 and 3 months or 0, 1, 3 and 6 months. Group 1 (CE/CE+gag) receives a combination of 2 immunogens for the boost. Group 2 (gag/gag) receives one immunogen as both the prime and the boost. Partially heterologous boost vaccinations are proposed in Group 1 to further increase the likelihood of robust immune responses.

4.6.3 Choice of control

Sodium Chloride for Injection, USP 0.9%, will serve as the placebo for the p24CE1/2 pDNA vaccine, the p55^{gag} pDNA vaccine, and *IL-12* pDNA. Sodium Chloride for Injection, USP 0.9% is nonreactogenic and well tolerated. It will be delivered by IM/EP as a control for blinding purposes. It is possible that the presence of bupivacaine in the vaccines and adjuvant may reduce the pain of injection reported on the VAS relative to the saline control. This should not adversely affect the efficiency of blinding.

4.7 Plans for future product development and testing

Positive results would prompt at least two avenues of future trials, towards evaluation of efficacy, either alone or in conjunction with other immunogens against other regions of the viral proteome, and for the development of additional CE immunogens corresponding to other regions of HIV-1 proteins and a therapeutic vaccine to target the highly conserved less exhausted epitopes of the HIV.

